test will be used to compare Q_{peak} *between* protocols, and the values obtained from the first vs the second Q_{CL} and Q_{step} tests will be used to determine the TE *within* each protocol. The VO_{2peak} from the VO_{2CL} and VO_{2step} protocols will be compared to the VO_{2peak} from the baseline VO_{2peak} test.

Participants will be instructed to maintain their habitual diet between testing sessions and abstain from strenuous exercise and alcohol consumption for a minimum of 24 hours before testing. A 24-hour dietary log will be completed before every experimental trial testing session.

Participants will be instructed to arrive to the laboratory hydrated. Testing sessions will take place at the same time of day ± 1 hour for each participant. All exercise protocols will use a cycle ergometer (Lode Excalibur Sport V2.0, Groningen, The Netherlands).

[figure not shown]

Figure 2: Schematic of study design. Q fam., cardiac output familiarization; Verif, Verification; h, hours. Each set of 2 experimental trials will be performed in random order.

Randomization

The order of the 6 experimental trials will be determined using simple randomization in Microsoft Excel. For each participant, a random, 15 decimal place number between 0 and 1 will be assigned to each experimental trial using the “=rand()” formula. The experimental trials will

be sorted using the “sort largest to smallest” function to determine the order in which the trials will be performed. The random sequence generation will be performed by a study investigator who is not involved in participant enrollment and will inform the other investigators of the order of experimental trials for each participant 24 hours before their first session. Due to the nature of the experiments, we are unable to blind the participants or researchers to the order of experimental tests; however, we will limit performance bias by blinding participants to the study hypotheses.

Primary outcome measure

Q_{peak} determined using the first Q_{CL} and Q_{step} protocols.

Secondary outcome measures

Reproducibility of Q_{peak} for each of the two IGR protocols based on the 1st and 2nd experimental trial for each test.

HR_{peak} determined during to the two IGR protocols.

$VO_{2\text{peak}}$, HR_{peak} , and W_{peak} determined during the baseline and verification $VO_{2\text{peak}}$ tests.

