$VO_{2\text{peak}}$ between the $VO_{2\text{peak}}$ test, the $VO_{2\text{CL}}$ protocol and the $VO_{2\text{step}}$ protocol.

$VO_{2\text{peak}}$ between the Q_{CL} vs $VO_{2\text{CL}}$ tests and the Q_{step} vs $VO_{2\text{step}}$ tests.

$VO_{2\text{peak}}$ tests

For the determination of $VO_{2\text{peak}}$, participants will perform a progressive exercise test to maximal voluntary exertion using an electromagnetically braked cycle ergometer (Lode Excalibur Sport V2.0, Groningen, The Netherlands). Following a 3 min warm-up at a fixed workload of 50 W, a ramp protocol will be applied with a linear workload increase of 1 W every 2 s (30 W/min). The

precise protocol will be standardized for a given participant and intend to achieve a ramp duration of ~10 min (range: 5-15 min). Pedaling cadence will be chosen by the participant and will be required to be ≥ 60 rpm. A 3-min recovery phase will be performed at 50 W. Gas exchange and ventilatory variables will be continuously determined using a metabolic cart (Quark CPET metabolic cart, COSMED, Italy). Data will be averaged over 10-s intervals and $VO_{2\text{peak}}$ will be defined as the highest 30-s average over three consecutive intervals. Heart rate will be recorded continuously (Polar A3, Finland) and HR_{peak} will be defined as the highest 2-s average. Data-based cutoffs for age-stratified secondary exhaustion criteria based on peak respiratory exchange ratio and age-predicted maximal heart rate (16) will be used to verify that the test involved maximal effort. The highest $VO_{2\text{peak}}$, HR_{peak} , and W_{peak} between the baseline and verification tests will be regarded as the ‘true’ peak.

Q_{CL} protocol

This protocol involves a ramp exercise test to exhaustion, followed by a constant work rate test that is initiated after 10 minutes of active recovery (Figure 3). The ramp phase uses the same protocol as the $VO_{2\text{peak}}$ test (described above). The constant work rate phase will begin with a 1-minute warmup at 50 W. The warmup will be followed by an immediate increase to an intensity equivalent to 90% of the W_{peak} elicited during the baseline ramp $VO_{2\text{peak}}$ test (90% W_{peak}). HR (Polar A3, Finland) and VO_2 (Innocor, COSMED, Italy) will be monitored continuously throughout the test. The rebreathing procedure to measure Q_{peak} (Innocor, COSMED, Italy) will be initiated after 2 minutes of cycling at 90% W_{peak} .

[figure not shown]

Figure 3: Q_{CL} protocol.

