Q_{step} protocol

This test is modelled after an incremental exercise protocol that has commonly been used to assess Q_{peak} (6, 15, 17) including to assess potential changes in Q_{peak} after an exercise intervention (15). The test will begin with a 3-minute warm-up at 50 W and workload will subsequently be increased by 30 W every 1 minute (Figure 4). HR (Polar A3, Finland) and VO_2 (Innocor, COSMED, Italy) will be monitored continuously throughout the test. The rebreathing procedure to measure Q_{peak} (Innocor, COSMED, Italy) will be initiated when the participant reaches a HR that is within 5 bpm of their previously determined HR_{peak} obtained from baseline VO_{2peak} testing (visit #1 or 3 from Figure 2). W_{peak} will be calculated as $W_{peak} = W_{completed} + 30 \times (t/60)$ where $W_{completed}$ is the last completed workload and t is the time in s maintained during the final workload.

[figure not shown]

Figure 4: Q_{step} protocol.

VO_{2CL} protocol

The VO_{2CL} protocol will be identical to the Q_{CL} protocol (Figure 3), except VO_2 will be monitored continuously using the same metabolic cart as the $VO_{2\text{peak}}$ test (Quark CPET metabolic cart, COSMED, Italy), and Q_{peak} will not be assessed. The constant load $90\% W_{\text{peak}}$ phase will be 2 min and 15 s in duration; the final 15 s is added to account for the approximate time it would take for the IGR to occur.

VO_{2step} protocol

The VO_{2step} protocol will be identical to the Q_{step} protocol (Figure 4), except VO₂ will be monitored continuously using the same metabolic cart as the VO_{2peak} test (Quark CPET metabolic cart, COSMED, Italy), and Q_{peak} will not be assessed. Participants will continue cycling for an additional 15 s after reaching a HR that is within 5 bpm of HR_{peak} to account for the approximate time it would take for the IGR to occur.

Statistical analysis

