A two-tailed paired samples t-test will be performed to compare each of Q_{peak}, HR_{peak}, and W_{peak} between the two experimental conditions (Q_{CL} vs Q_{step}). A two-tailed paired samples t-test will be performed to compare each of VO_{2peak}, HR_{peak}, and W_{peak} between the baseline and verification VO_{2peak} tests, to compare Q_{peak} between the first and second Q_{CL} and Q_{step} tests, and to compare VO_{2peak} between the VO_{2peak} test and each of VO_{2CL} and VO_{2step}. Significance will be set to p<0.05. Effect sizes will be reported as Cohen's d_z and 95% confidence intervals (CI) will also be determined. Q_{peak} estimated by the Q_{CL} protocol will be considered noninferior to the Q_{step} protocol if the 95% CIs for the change in Q_{peak} fall within the margin of noninferiority (i.e., 0.5 L/min) (18, 19).

Reliability of each experimental protocol and of the VO_{2peak} tests will be calculated as the TE using the following formula (20):

$$TE = (SD_{diff} \div \sqrt{2} \div grand\ mean) \times 100$$

Where SD_{diff} is the standard deviation of the difference scores between the 2 measurements, and the grand mean is the mean of all measurements included in the analysis. The TE will be expressed as a percentage.

Perspectives and significance

IGR provides a noninvasive method for determining Q_{peak} , and assessing potential changes elicited by acute and chronic exercise interventions. The proposed work will systematically compare two methods for determining IGR-derived Q_{peak} , to assess potential differences between protocols as well as reliability of each method. This research will provide novel comparative data and inform decisions by researchers regarding choice of Q_{peak} protocol in future studies.

Strategies to reduce bias

Selection bias

The order of experimental trials will be randomized for each participant using Microsoft Excel by an investigator not involved in participant enrollment. This investigator will inform the other investigators of the trial order after baseline testing, and 24 hours before the first experimental trial for each participant. The investigator performing the randomization will play a secondary role in data collection.

Performance and detection bias

Given the distinct nature of each experiment, it is not possible to blind investigators or participants to the order of experimental trials. However, we will limit performance bias by blinding participants to the study hypotheses.

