Reporting bias

The current protocol, which clearly states the primary and secondary outcomes and hypotheses, will be published in an open access repository prior to participant recruitment.

Summary of analysis plan

| Question | Hypothesis | Data collection plan | Analysis plan | Interpretation |
|---|--|---|--|--|
| Is Q_{peak} determined by Q_{CL} noninferior to Q_{step} ? | Q_{CL} is noninferior to Q_{step} . | Measure Q_{peak} following Q_{CL} and Q_{step} using a randomized within-subject design. | Calculate 95% CIs for the mean difference in Q_{peak} between Q_{CL} and Q_{step} . | Q_{CL} is noninferior to Q_{step} if the lower bound of the CI is within 0.5 L/min. |
| What is the reproducibility of the Q_{CL} and Q_{step} protocols? | Reproducibility will be similar between Q_{CL} and Q_{step} . | Measure Q_{peak} during 2 Q_{CL} tests and 2 Q_{step} tests in a randomized order. | Calculate the TE between 1) the 2 Q_{CL} tests, and 2) the 2 Q_{step} tests. | Result will provide an indication of Q_{peak} reproducibility. |
| Is the HR_{peak} different between Q_{CL} and Q_{step} ? | HR_{peak} will not be significantly different between Q_{CL} and Q_{step} . | Measure HR_{peak} during Q_{CL} and Q_{step} using a randomized within-subject design. | Perform a paired t-test for HR_{peak} between Q_{CL} and Q_{step} . | If HR_{peak} is not significantly different between Q_{CL} and Q_{step} , it suggests participants are similarly close to “max” values during both protocols. |
| What is the reproducibility of the $VO_{2\text{peak}}$ test? | The reproducibility for the $VO_{2\text{peak}}$ tests will be approximately 5%. | Measure $VO_{2\text{peak}}$ during the baseline and verification $VO_{2\text{peak}}$ tests. | Calculate the TE of the baseline and verification $VO_{2\text{peak}}$ tests. | Result will provide an indication of $VO_{2\text{peak}}$ test reproducibility. |

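### The HR_peak comparison is not tied to the moment cardiac output is measured, so a non-significant t-test need not show that participants are similarly close to maximum at rebreathing

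*Protocol*

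**What the plan says.** - **Decision rule.** The HR_peak row of the Summary of analysis plan specifies a paired t-test of HR_peak, Q_CL against Q_step. If the result is not significant, "it suggests participants are similarly close to “max” values during both protocols". The Statistical analysis section makes the test two-tailed and adds: "Significance will be set to p<0.05".
- **Definition.** The only definition is in the VO2peak tests section: "HR_{peak} will be defined as the highest 2-s average". The secondary outcome is listed as "HR_{peak} determined during to the two IGR protocols", with no phase or time window.
- **Q_CL.** "This protocol involves a ramp exercise test to exhaustion, followed by a constant work rate test". The constant phase follows 10 minutes of active recovery, opens with 1 minute at 50 W, then moves to 90% W_peak. Rebreathing starts after 2 minutes at that load. HR is monitored over the whole test.
- **Q_step.** Rebreathing "will be initiated when the participant reaches a HR that is within 5 bpm of their previously determined" HR_peak from baseline testing.
- **Objective.** Secondary objective 2 asks whether VO2 and HR from the two experimental protocols differ from the baseline peak values.
- **Expected constant-load HR.** The Background puts HR in constant-load exercise above 85% W_peak within about 5% of the value at the end of a ramp test.

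**The concern.** The row is meant to support reading both protocols as measuring cardiac output near maximum. That requires heart rate at rebreathing. If the highest 2-s average is taken over the whole Q_CL session, the ramp to exhaustion will normally supply it, and heart rate in the constant-load phase drops out of the comparison. On the other side, Q_step heart rate has to reach a threshold near maximum before any measurement is made, so its closeness to maximum is largely an entry condition.

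The conclusion about Q_CL could then be wrong in either direction. The protocols could be called similar when Q_CL heart rate at rebreathing is clearly lower. They could also be called different, with Q_CL higher, only because the ramp is compared with a test measured just short of maximum.

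**Working it through.** **1. Time between the ramp and the measurement (Q_CL protocol section).** 10 min recovery + 1 min warm-up + 2 min at 90% W_peak = 13 min from the end of the ramp to the start of rebreathing.

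**2. What enters the t-test.** Let R be the peak HR in the Q_CL ramp, C the HR in the constant-load phase and S the HR in Q_step.
- Whole-session reading: the test uses max(R, C) − S. When C < R this equals R − S, and C has no influence.
- Constant-load reading: the test uses C − S, which does carry the needed information.

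**3. Size of the shortfall the protocol itself allows.** About 5% of an assumed maximum of 180, 190 or 200 bpm is 9.0, 9.5 or 10.0 bpm. At 190 bpm that is 9.5 / 5 = 1.9 times the Q_step window.

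**4. Worked example (assumed maximum 190 bpm).** R = 190, C = 190 − 9.5 = 180.5.
- If S = 190: whole-session difference 190 − 190 = 0; difference at rebreathing 180.5 − 190 = −9.5 bpm.
- If S = 187.5 (midpoint of the 5 bpm window): whole-session difference +2.5; difference at rebreathing −7.0 bpm. The sign reverses.

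**5. Sample size.** The HR row states no figure. The protocol's n = 34 (two-tailed paired t-test, d_z = 0.5, 80% power, alpha 0.05) reproduces with the noncentral t: power at n = 34 is 0.808. At 80% power the detectable d_z is 0.495. For an assumed SD of the paired HR difference of 3, 5 or 8 bpm, that is 0.495 × SD = 1.5, 2.5 or 4.0 bpm. A 9.5 bpm difference would therefore be found if constant-load HR were the variable tested.

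**6. Illustration by simulation.** 20,000 trials of n = 34, constant-load HR 9.5 bpm below maximum, normal day-to-day variation. Q_step HR is uniform over the stated range relative to the reference, plus noise of SD 1 bpm. None of these SDs or ranges is in the protocol.

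| Q_step HR relative to reference | Day-to-day SD (bpm) | P(non-significant), whole session | P(non-significant), constant-load HR |
|---|---|---|---|
| −2 to +2 | 2 / 3 / 4 | 0.951 / 0.949 / 0.947 | 0.000 / 0.000 / 0.000 |
| −5 to 0 | 2 / 3 / 4 | 0.000 / 0.015 / 0.062 | 0.000 / 0.000 / 0.000 |

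In the second row the whole-session mean difference is +2.5 to +2.6 bpm, while the difference at rebreathing is −7.0 bpm. Under another set of assumptions (Q_step HR at reference − 5 plus a mean rise of 1 to 3 bpm, SD 2 to 4, ramp supplying the Q_CL peak), the non-significant proportion ran from 0.000 to 0.942. On the whole-session reading, the result follows the assumed Q_step heart rate and not the constant-load heart rate.

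**7. Objective against analysis.** The Statistical analysis section tests HR_peak for Q_CL against Q_step and for baseline against verification. It compares VO2peak, but not HR, with the baseline test. The Summary of analysis plan follows the same pattern. No HR analysis against baseline is specified for secondary objective 2.

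**The case against.** The strongest objection is that the ramp as source is an inference. The definition stands under the VO2peak tests, not under Q_CL. Rebreathing in Q_CL happens only in the constant-load phase, the Background treats constant-load HR as distinct from ramp-end HR, and secondary objective 2 would be nearly trivial if the ramp inside Q_CL counted. VO2_CL adds 15 s to its constant-load phase to stand in for rebreathing. All of this suggests the constant-load phase was intended, and on that reading the comparison works. This stands in part. The documents do not support saying that the rule can never show closeness to maximum. But other text points the other way: HR is monitored throughout, and W_peak is also compared between Q_CL and Q_step although the constant load is preset at 90% of baseline W_peak, so a measured Q_CL W_peak would have to come from the ramp. No sentence settles it.

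A reader might also infer that Q_step HR is fixed by its trigger. It is not. The trigger sets a floor of baseline HR_peak − 5 bpm at the start of rebreathing; HR may rise further, and the protocol does not say by how much.

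Finally, an extraction window for a secondary variable is often left to a statistical analysis plan. Here, however, the protocol states the definition, the test and the interpretation, and taken together literally they can give a wrong conclusion.

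**Conclusion.** The point holds in limited form. The HR_peak row does not tie heart rate to the moment cardiac output is measured. On the only stated definition the ramp would normally supply the Q_CL value, and Q_step HR is constrained from below by its trigger. Read that way, a non-significant t-test does not establish that participants are similarly close to maximum at rebreathing, and it can miss a shortfall of about 5% (9 to 10 bpm at an assumed maximum of 180 to 200 bpm). If constant-load HR is meant, the comparison is informative and the gap is one of wording. Separately, secondary objective 2 has no HR analysis against baseline.

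The simulated proportions rest on assumed SDs and heart-rate rises. They illustrate the mechanism and should not be read as an error rate for this trial. The row is secondary and its interpretation is hedged. The primary noninferiority decision, the sample size and the typical error are not affected. The change should be made, because an open window could otherwise be settled after the data are seen.

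**What to change.** 1. Define the HR analysed in this row as HR at rebreathing, over a short stated window: the constant-load phase for Q_CL, with the ramp excluded, and the trigger point for Q_step.
2. For each protocol, report that HR minus the reference HR_peak (the higher of the baseline and verification tests) with its 95% CI. This also supplies the HR analysis that secondary objective 2 asks for.
3. Base the close-to-maximum conclusion for Q_CL on that difference and its interval, with what counts as close stated in advance, and not on a non-significant Q_CL against Q_step t-test.
4. State that Q_step HR is constrained by its trigger, so it mainly checks that the trigger was met.

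Cost: edits to the secondary outcome list, the Statistical analysis section and the HR_peak row. HR is already recorded continuously, so no visits, procedures or participants are added. The downside is that the reported Q_CL HR may be lower than the whole-session peak.

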Objectives

Primary objective

To test whether the Q_{peak} produced from the Q_{CL} protocol is not meaningfully different from the Q_{step} protocol using a non-inferiority design.

Secondary objectives

(1) to determine the reliability of the Q_{CL} and Q_{step} protocols, (2) to determine whether the VO_2 and HR obtained from the two experimental protocols are not different from the $VO_{2\text{peak}}$ and HR_{peak} obtained from the baseline $VO_{2\text{peak}}$ test, and (3) to determine whether the VO_2 measured by the Innocor is lower than the metabolic cart.

Hypothesis

We hypothesize that the Q_{CL} protocol will produce a Q_{peak} that is not different (by a margin of noninferiority of 0.5 L/min) compared to the Q_{step} protocol. A Q_{peak} of 0.5 L/min was the TE in a previous study in our laboratory (9), and is therefore deemed to be the minimum meaningful difference for determinations of Q_{peak} .

Methods

Participants

Participants will be recruited from the McMaster community and surrounding area through printed posters, web-based advertisements, and word of mouth.

Inclusion criteria:

- Adults aged 18-35 years.
- Meeting the Canadian 24-hour Movement Guidelines for Adults for aerobic physical activity, i.e. ≥ 150 minutes of moderate to vigorous activity per week (13). This will be assessed using the Canadian Society for Exercise Physiology Get Active Questionnaire (GAQ) (14).

Exclusion criteria:

- Diagnosis of any cardiovascular, respiratory, or metabolic disease that would preclude participation from a clinical standpoint, as determined by answering ‘yes’ to any of the questions on the first page of the GAQ.

Details of the experimental protocol, purpose and potential risks of participation will be explained to all participants and written informed consent will be obtained prior to participation in the study. This study has been approved by the Hamilton Integrated Research Ethics Board (Project # 13339).

Sample size determination

A calculation performed using G*Power (v 3.1.9.2) for a two-tailed dependent means (matched pairs) t-test estimated that a sample size of 34 was required to detect a medium effect size ($d_z=0.5$) with 80% power at an alpha level of 0.05 (Figure 1). A medium effect size was deemed

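### A non-significant t-test on HR_peak is read as both protocols being similarly close to maximum, and the planned analyses leave out the HR comparison with baseline that secondary objective 2 asks for

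*Protocol*

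**What the plan says.** The HR_peak row of the Summary of analysis plan takes the null result as its hypothesis: "HR_{peak} will not be significantly different between Q_{CL} and Q_{step". The analysis is "Perform a paired t-test for HR_{peak} between Q_{CL} and Q_{step". The interpretation covers one case only: if the difference is not significant, "it suggests participants are similarly close to" maximal values during both protocols. No HR margin is given there or elsewhere. The Q_peak and VO2peak rows of the same table that ask about noninferiority use a 95% CI against a margin (0.5 L/min and 0.2 L/min).

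Secondary objective 2 is "to determine whether the VO_2 and HR obtained from the two experimental protocols are not different from the" baseline VO2peak and HR_peak. The Statistical analysis section plans t-tests "to compare each of Q_{peak}, HR_{peak}, and W_{peak} between the two experimental conditions", and tests HR_peak again between the baseline and verification tests. Its comparison of the experimental protocols with baseline names VO2peak alone.

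Two other places bear on HR. In the Q_step protocol, rebreathing starts when the participant's HR is "within 5 bpm of their previously determined HR_{peak". The Background reports that constant-load exercise above 85% W_peak gives HR within about 5% of the value at the end of a ramp test.

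**The concern.** There are two faults of inference and one gap.

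- A t-test that fails to reject can mean that the difference is small or that the data are too imprecise to show it. The HR row reads both cases the same way.
- Q_CL versus Q_step can show whether the two protocols are alike. It cannot show how far either lies below maximum, since both could fall short by the same amount. The Q_step trigger permits a shortfall of up to 5 bpm, and the Background figure makes one foreseeable for Q_CL.
- The comparison that would address closeness to maximum, each protocol against baseline HR_peak, is an objective with no analysis attached.

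At stake is what may be said about HR as supporting evidence that Q_peak was measured near maximum in both protocols.

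**Working it through.** **Inputs.** n = 34, two-tailed paired t-test, alpha 0.05, d_z = 0.5 and 80% power come from Sample size determination. The SD of paired HR differences (SD_diff) is not in the protocol, so 4 to 10 bpm is assumed.

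**The plan's own figure.** Exact noncentral-t power for a two-sided paired test at d_z = 0.5 first reaches 80% at n = 34 (power 0.808). The stated sample size is reproduced.

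**What a non-significant HR result allows.** The 95% CI half-width is t(0.975, 33) / √34 × SD_diff = 0.349 × SD_diff. The result is non-significant when the observed difference is below this half-width. The far CI limit is then below 2 × 0.349 × SD_diff = 0.698 × SD_diff.

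| Assumed SD_diff (bpm) | Largest non-significant observed difference | Furthest CI limit |
|---|---|---|
| 4 | 1.40 | 2.79 |
| 6 | 2.09 | 4.19 |
| 8 | 2.79 | 5.58 |
| 10 | 3.49 | 6.98 |

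The limit can pass 5 bpm only if SD_diff exceeds 5 / 0.698 ≈ 7.2 bpm. Example at SD_diff 8: an observed 2.5 bpm has a CI of 2.5 ± 2.79, or −0.3 to 5.3 bpm. The row would read this as similar.

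**How often a real gap is missed.** A true 3 bpm difference is non-significant with probability 0.076 at SD_diff 5, 0.435 at 8 and 0.603 at 10.

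**Whether a CI rule is feasible at n = 34.** The probability that the 95% CI lies wholly inside the margin, with no true difference (simulated):

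| Margin | SD_diff 5 | 7 | 8 | 10 |
|---|---|---|---|---|
| ±5 bpm | 1.00 | 0.96 | 0.89 | 0.62 |
| ±3 bpm | 0.85 | 0.36 | 0.16 | 0.01 |

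**Objective 2 set against the analyses (each protocol versus baseline).**

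| Place in the protocol | VO2 | HR |
|---|---|---|
| Secondary objective 2 | asked | asked |
| Secondary outcome measures | VO2peak test against VO2_CL and VO2_step | HR_peak in the two protocols, no comparison with baseline |
| Statistical analysis | paired t-tests | none |
| Summary of analysis plan | 95% CI, 0.2 L/min | none |

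**Which HR counts as Q_CL HR_peak.** The VO2peak tests section defines HR_peak as the highest 2-s average. Q_CL contains a ramp to exhaustion before the constant-load phase in which rebreathing occurs. Taken over the whole Q_CL session, HR_peak could come from the ramp and say nothing about HR when Q was measured.

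**The case against.** The case for leaving the row alone has several parts.

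- The wording is cautious (it says that the result suggests similarity), and Statistical analysis promises 95% CIs. This stands: the data for a proper judgement will exist, and the fault lies in the stated rule.
- If SD_diff is under about 7.2 bpm, a non-significant result does exclude 5 bpm. This also stands. At SD_diff 8, the limit passes 5 bpm only for observed differences between 5 − 2.79 = 2.21 and 2.79 bpm. But the protocol gives no SD and no HR margin, so the reader cannot know in advance that non-significance will be informative.
- Experimental procedures says that the highest baseline values will serve for comparison with the main trials, and an unseen SAP could name the test. This softens the gap. The mismatch remains, because the protocol specifies the VO2 half of the objective twice and the HR half not at all.
- In Q_step the trigger largely fixes HR near HR_peak, so the check against baseline is close to automatic there. It is informative mainly for Q_CL.

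A reader might infer more than the text supports:

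- **That a significant but trivial HR difference counts as failure.** The row interprets only the non-significant case.
- **That HR is the plan's only evidence of near-maximal effort.** A separate row compares VO2_CL and VO2_step with baseline VO2peak by a CI rule.
- **That the VO2peak t-test and the 0.2 L/min rule conflict.** No noninferiority decision is attached to the t-test, the table gives the only decision rule, and a result can coherently be both significantly lower and noninferior.
- **That 5 bpm is the plan's own tolerance for a mean difference.** It is an individual trigger for rebreathing in Q_step.

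**Conclusion.** The point holds for the HR row and for the HR half of objective 2. As written, the rule can describe the protocols as similarly close to maximum while the CI for their difference extends to 0.70 × SD_diff, and without any reference to maximum. Whether that is material depends on SD_diff, which is assumed here. Against 5 bpm it matters above about 7.2 bpm (5.6 bpm at 8, 7.0 bpm at 10). The logical fault, using a between-protocol comparison to speak about closeness to maximum, does not depend on SD_diff. The outcome is secondary and the primary rule for Q_peak does not use it. The change is worth making but is not critical.

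**What to change.** Replace the interpretation in the HR_peak row with a rule of this form: HR is considered similar if the 95% CI for the mean difference lies within a pre-specified margin. Apply it to Q_CL versus Q_step and to each protocol versus baseline HR_peak, adding a table row and a sentence in Statistical analysis for the latter. State that Q_CL HR is taken from the constant-load phase at rebreathing, not from the preceding ramp. The HR t-test may stay as a descriptive result.

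The margin has to be argued. Five bpm is one candidate, but the protocol uses it as a per-participant trigger. The Background's figure of about 5% would be roughly 9.5 bpm at an assumed HR of 190 bpm (0.05 × 190). At an assumed stroke volume of 100 mL, 5 bpm × 0.100 L = 0.5 L/min, the whole Q_peak margin, and this scales in proportion to the stroke volume assumed.

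The cost is about two table rows, one or two sentences and a justified margin, with no added visits or participants. The downside is that similarity may be left unproven if SD_diff is large. With a ±5 bpm margin and no true difference, the chance of showing it is 0.89 at SD_diff 8 but 0.62 at 10. A narrower margin, or a real difference, would lower it.
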